A random population of 200 CT scans of pelvis and thigh in an adult population affected by hip dysplasia will be selected. The aim of this study is to evaluate the biomechanical reconstruction of the hip anatomy provided by three different hip stem designs in dysplastic cases, using a 3D CT based software for pre-operative planning. Pre-operative planning in hip arthroplasty with dedicated software is a useful guide to provide a better reconstruction of the biomechanical parameters of the replaced hip and to optimize the choice of component, improving the geometric understanding of the hip anatomy and the interaction between the native morphological structure and the prosthetic component. The use of a 3D CT-based software for pre-operative planning may provide a better knowledge of the hip anatomy, simulating the biomechanical parameters more closely than a 2D X-ray-based software. In addition, it is the only way to anticipate the correct interaction between the prosthetic components, or the combined anteversion, a key factor in preventing implant instability. Severe hip deformities, like developmental hip dysplasia, may not be adequately reconstructed by every implant and 3D pre-operative CT may increase the three-dimensional anatomical knowledge of the hip, improving the choice of the correct implant and possibly reducing the possible consequences of intra and post-operative complications. Therefore, the purpose of this study is to pre-operatively plan, in a random series of 200 native pelvis and thigh CT scans performed in patients with hip dysplasia, 3 different types of hip stem designs using the 3D Hip-Op software, with the aim of analyzing, on the CT simulations, the percentage of adequate reconstruction of the optimal biomechanical parameters (combined anteversion between 25°-50°, global offset not inferior to 12% of the native offset, leg lengthening not superior to 3 cm, sagittal and coronal tilt not superior to +/-5°, canal filling not inferior to 80%). The percentage of every stem design providing the optimal reconstruction in dysplastic hips (all the 5 parameters matched) will be assessed. The single parameters, especially the combined anteversion, the offset restoration and the leg lengthening, will be assessed for every simulation.

STATISTICAL ANALYSIS

The analyses were performed using SPSS 14.0 (SPSS Inc, Chicago, IL). Quantitative data were reported as average values, standard deviations and ranges of minimum and maximum. Qualitative data were expressed as frequencies and percentages and tested using chi-squared test. The reliability of the simulations was assessed using Fisher test (categorical variables). Threshold for significance: $p=0.05$.

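### Read literally, the offset criterion passes any plan that keeps 12% of native offset, so the five-parameter composite is in effect a four-item score

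*Combined protocol and SAP*

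**What the plan says.** The unnumbered study description in the combined protocol and SAP lists five parameters that define an optimal reconstruction:

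- "combined anteversion between 25°-50" degrees
- "global offset not inferior to 12% of the native offset"
- "leg lengthening not superior to 3 cm"
- "sagittal and coronal tilt not superior to +/-5" degrees (one item, to reach the plan's count of five)
- "canal filling not inferior to 80" per cent

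These feed a composite in which every item must be met: "The percentage of every stem design providing the optimal reconstruction in dysplastic hips (all the 5 parameters matched) will be assessed". Offset is also a named single parameter: "The single parameters, especially the combined anteversion, the offset restoration and the leg lengthening, will be assessed for every simulation". The Statistical Analysis section adds that "Quantitative data were reported as average values, standard deviations and ranges of minimum and maximum", and that qualitative data are summarised as percentages and compared by chi-squared test. Neither section defines or restates the offset rule.

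**The concern.** As worded, the offset item sets a minimum of 12% of native and no maximum. The canal-filling item in the same list uses the same phrase as a plain floor, which supports the literal reading. A floor this low would exclude almost nothing.

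The main result is the percentage of plans, per stem, that meet all five items. An item that nearly every plan meets drops out of an all-must-pass score. The composite could then not be lower than under any stricter offset rule, and a stem that restored offset poorly would not be marked down for it. The offset pass rate would sit near 100% for every stem, which leaves the chi-squared test nothing to compare.

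The wording also leaves at least three readings open: a share of native offset, a permitted loss from it, or a deviation in either direction. Two people could classify the same simulation differently.

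**Working it through.** The plan gives no expected rate, power or sample-size figure that depends on this criterion, so there is no stated figure to reproduce. The check asks how often the item could fail under each reading.

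**Inputs from the documents:** 200 scans; three stem designs; the cut-off 12%; the rule that all five items must be met.

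**Assumptions (no offset distribution is given):** the ratio R = planned offset / native offset is normal with mean m and SD s. The other four items are jointly met in p4 = 70% of plans (illustrative).

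**1. What the cut-offs mean.** Literal reading: R ≥ 0.12, a loss of up to 1 − 0.12 = 88%. Permitted-loss reading: R ≥ 1 − 0.12 = 0.88. For assumed native offsets of 40 to 80 mm, the literal floor is 0.12 × 40 = 4.8 mm to 0.12 × 80 = 9.6 mm. The permitted-loss floor is 0.88 × 40 = 35.2 mm to 0.88 × 80 = 70.4 mm.

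**2. Failure rates.** P(fail) = Φ((c − m)/s), with c = 0.12 or 0.88.

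| m | s | Fail, c = 0.12 | Per 200 | Fail, c = 0.88 | Per 200 |
|---|---|---|---|---|---|
| 1.0 | 0.15 | 2.2 × 10⁻⁹ | 0.000 | 21.2% | 42.4 |
| 1.0 | 0.20 | 5.4 × 10⁻⁶ | 0.001 | 27.4% | 54.9 |
| 1.0 | 0.30 | 0.17% | 0.3 | 34.5% | 68.9 |
| 0.9 | 0.15 | 1.0 × 10⁻⁷ | 0.000 | 44.7% | 89.4 |
| 0.9 | 0.20 | 0.005% | 0.01 | 46.0% | 92.0 |
| 0.9 | 0.30 | 0.47% | 0.9 | 47.3% | 94.7 |
| 0.8 | 0.30 | 1.17% | 2.3 | 60.5% | 121.0 |

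The last row is the most extreme case for the literal rule: (0.12 − 0.80)/0.30 = −2.27, and 98.8% still pass.

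**3. Separation of two illustrative stems** (m = 1.0 and 0.9, s = 0.15):

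- Literal: both pass about 200 of 200.
- Loss of no more than 12%: Φ(0.80) = 78.8%, or 158 of 200, against Φ(0.133) = 55.3%, or 111 of 200. The gap is 23.5 points.
- Deviation within ±12%: 2Φ(0.80) − 1 = 57.6%, against Φ(1.467) − Φ(−0.133) = 48.2%. The gap is about 9 points.

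**4. Effect on the composite.** Let q be the offset pass rate. Without assuming independence, the composite lies between max(0, p4 + q − 1) and min(p4, q).

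- Literal: q is at least 98.8%, so the composite is within 1.2 points of p4, here about 70%.
- Permitted loss, q = 78.8%: from 0.70 + 0.788 − 1 = 48.8% to 70%. The literal figure is higher by 0 to 21 points. Under independence the composite is 0.70 × 0.788 = 55.2%, a difference of about 15 points.
- Permitted loss, q = 55.3%: from 0.70 + 0.553 − 1 = 25.3% to 55.3%. The literal figure is higher by 15 to 45 points. Under independence the composite is 0.70 × 0.553 = 38.7%, a difference of about 31 points.

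**The case against.** The strongest reply is that this is a drafting slip that nobody would score literally. The plan calls the list optimal and speaks of offset restoration, which fits poorly with accepting an 88% loss, and the neighbouring tilt item uses similar phrasing for a tolerance. A slip is probable. But the tilt item carries an explicit plus-or-minus sign and the offset item does not. A reader who rejects the literal text must still choose between a one-sided loss and a two-sided deviation, and step 3 shows that the choice matters.

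A second reply is that no effect on results is shown. That stands: the documents do not reveal which rule is scored. The composite differences are illustrative, and the 45-point end needs the least favourable joint distribution. Only the near-100% literal pass rate is insensitive to the assumptions.

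A third reply is that offset is also assessed on its own, with means, SDs and ranges, so a difference between stems could still be seen. That stands too, but those summaries do not repair the composite or the offset pass rate.

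**Conclusion.** The concern holds. The only offset rule in the documents is, as worded, one that almost no plan can fail: 0 to 2.3 expected failures per 200 for mean ratios of 80–100% and SDs of 10–30%. This needs only that planned offset be of the same order as native offset. Scored that way, the five-item composite reduces to the other four items to within about 1 percentage point.

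What is established is a defective threshold in the all-five composite and in a named single parameter. The size of any overstatement is unknown, and it is zero if a 12% loss is already being scored. No bias between stems is shown. The point must be fixed because the text does not settle how the item is scored.

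**What to change.** The sponsor should restate the offset criterion so that the reference value, the direction of the 12% and any upper limit are explicit. One possible form is a reduction of global offset by no more than 12% of native, if the sponsor confirms that this was the intended tolerance. If a two-sided deviation was meant, the text should say so. This review does not choose between them.

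The same rule should then be used for the offset item and for the composite. Ideally it is fixed before scoring. The Statistical Analysis section is in the past tense, so if scoring is already done, the report should state which rule was applied and recode if it was the literal one.

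The cost is one line of wording and, at most, recoding of a variable already measured. No new simulations are needed. The reported success percentage may be less favourable.

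### Three stems appear to be planned on the same 200 scans, but only unpaired tests are named; chi-squared between stems would ignore the matching and probably lose power

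*Combined protocol and SAP*

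**What the plan says.** The opening study description selects one sample of 200 scans and plans, in "a random series of 200 native pelvis and thigh CT scans performed in patients with hip dysplasia, 3 different types of hip stem designs". It describes no allocation of scans to stems. The main categorical outcome is pass or fail on all five biomechanical criteria, summarised by stem: "The percentage of every stem design providing the optimal reconstruction in dysplastic hips (all the 5 parameters matched) will be assessed". The criteria are also examined one at a time: "The single parameters, especially the combined anteversion, the offset restoration and the leg lengthening, will be assessed for every simulation".

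The STATISTICAL ANALYSIS section names two tests. The first is general: "Qualitative data were expressed as frequencies and percentages and tested using chi-squared test". The second has a stated purpose: "The reliability of the simulations was assessed using Fisher test (categorical variables". Quantitative data are only described. The significance threshold is 0.05. The section does not mention matching, does not say which contrast chi-squared tests, and names no paired method.

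**The concern.** If every scan is planned with all three stems, the data are 200 matched triplets, or 200 × 3 = 600 simulations on 200 anatomies. Chi-squared and Fisher both assume independent observations. Chi-squared is the only test named for qualitative data that is not tied to reliability, and the percentage per stem is the main qualitative outcome. The likely reading is therefore that chi-squared compares the stems, although the plan does not say so.

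A hip that is hard to reconstruct with one stem is plausibly hard with the others, which means positive correlation within hip. Chi-squared then overstates the variance of the differences between stems and rejects too rarely. At stake is the study's central question: a non-significant result could be read as the stems performing alike when the test has simply missed a difference.

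**Working it through.** **Inputs from the documents.** 200 scans, three stems and a threshold of 0.05. The plan gives no power, expected rates or sample-size calculation, so there is no figure to reproduce.

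**Assumptions.** Pass rates, and phi, the correlation between the pass/fail results of two stems on the same hip (taken as common to all pairs). Neither is in the documents, so ranges are shown.

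**1. True size of the three-stem chi-squared test.** With equal pass rates, the 3×2 statistic behaves as (1 − phi) times a chi-squared variable on 2 df. The 5% critical value is 5.991, so

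size = exp(−5.991 / [2(1 − phi)]).

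At phi 0.3 this is exp(−5.991/1.4) = exp(−4.279) = 1.4%.

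**2. Scan equivalents at 80% power.** The noncentrality needed on 2 df is 9.63 at critical value 5.991. At phi 0.3 chi-squared in effect faces 5.991/0.7, which needs 13.04. The ratio is 13.04/9.63 = 1.353, so 200 scans analysed with chi-squared are worth 200/1.353 = 148 analysed with Cochran's Q.

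**3. Power at 200 scans, assumed rates 60/60/70%.** From 20,000 simulated trials per phi, with correlated latent normal variables matched to phi.

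| phi | true size, chi-squared | scan equivalent of 200 | power, chi-squared | power, Q |
|---|---|---|---|---|
| 0 | 5.0% | 200 | – | – |
| 0.1 | 3.6% | 183 | 56% | 61% |
| 0.2 | 2.4% | 166 | 56% | 68% |
| 0.3 | 1.4% | 148 | 55% | 74% |
| 0.5 | 0.25% | 111 | 54% | 88% |

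Simulated size (65% pass rate) was 5.2 / 3.5 / 2.6 / 1.4 / 0.24% for chi-squared over the same phi values; Q stayed within 4.7–5.3%. At phi −0.2 the formula gives 8.2%, so the error would reverse.

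**4. Other assumed rates** (chi-squared v Q).

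| rates | phi 0.1 | phi 0.3 |
|---|---|---|
| 40/40/50% | – | 51 v 70% |
| 80/80/90% | – | 86 v 95% |
| 60/60/75% | 93 v 95% | 95 v 98.5% |
| 60/60/80% | at least 99.8% for both | at least 99.8% for both |

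**5. A worked result.** Suppose the stems pass 120, 120 and 138 of 200, with phi 0.3.

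- Chi-squared: the mean is 126 and the pooled rate 0.63. The statistic is (6² + 6² + 12²)/(200 × 0.63 × 0.37) = 216/46.62 = 4.63, p = 0.099.
- Cochran's Q = 2(3ΣT² − G²)/(3G − Σr²), where T is a stem's passes, G the total passes and r the passes per hip. Here G = 378 and ΣT² = 47,844, so the numerator is 2(143,532 − 142,884) = 1,296. The expected joint passes over the three pairs sum to 279.2, so Σr² = 378 + 2 × 279.2 = 936.4 and the denominator is 1,134 − 936.4 = 197.6. Q = 6.56, p = 0.038.

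Chi-squared first reaches significance at 141 passes for the third stem. Q does so at 140 / 139 / 138 / 135 for phi 0.1 / 0.2 / 0.3 / 0.5. With the two equal stems anywhere from 80 to 160 passes, the window in which the verdicts differ is 1–2 passes wide at phi 0.1, 3–4 at 0.3 and 5–7 at 0.5. These windows use expected joint counts, a common phi and two equal stems; observed counts will vary around them.

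**The case against.** The strongest reply is that the point rests on three inferences: that every stem is planned on every scan, that chi-squared compares the stems, and that phi is positive and not trivial. The plan states none of them, and its outcome is worded descriptively. On that view the plan has a gap in clarity, not a demonstrated wrong test. The first two inferences are nevertheless the natural reading. If chi-squared serves some other purpose, the plan has no test for its central comparison, and the section needs the same clarification.

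The objection on size stands in part. The choice of test matters most for differences of about 10 points and hardly at all for 15 to 20 points, and nothing in the documents says which is relevant. High correlations are also unattainable when stems differ strongly: phi cannot exceed √(0.6 × 0.1 / (0.4 × 0.9)) = 0.41 for rates of 60% and 90%. The description also allows that different implants may suit different hips, which could pull phi towards zero. These points limit the loss; they do not make an independence test right for matched data.

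Finally, under positive phi false positives fall below 5% and the reported percentages are unchanged. That is correct, and it limits how serious the problem is.

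**Conclusion.** The concern holds, conditionally on the matched reading and on chi-squared being the test between stems. Its direction depends on positive within-hip correlation, which is plausible but undocumented. For phi from 0.1 to 0.5, chi-squared has a true size of 3.6% down to 0.25%, and 200 scans do the work of 183 down to 111. For a 10-point difference at 60/60/70%, the loss is about 5 to 34 percentage points of power. It is negligible at phi near 0 and small for clearly larger differences. A significant overall result can be trusted under positive phi; a non-significant one is weaker evidence than it looks. This should be fixed, but it does not undermine the descriptive results.

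**What to change.** State in STATISTICAL ANALYSIS that each scan is planned with all three stems and that the test compares stems. Then replace chi-squared for that comparison, for example:

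> The proportion of hips meeting all five criteria (main comparison) is compared between the three stems with Cochran's Q at 0.05. Only if Q is significant are the three pairwise McNemar tests done, each at 0.05. Paired differences in percentages are given with matched-pairs 95% confidence intervals. Each single criterion is analysed in the same way as a secondary outcome.

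The gate is needed. With all stems equal, three ungated McNemar tests gave at least one false positive in 12.1–12.8% of simulated trials, against 4.7–5.3% when gated by Q. Holm-adjusted McNemar tests (4.1–4.5%) are an alternative.

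If both hips of a patient may enter, use a method clustered on patient, such as logistic GEE with stem as a factor and robust variance. If scans were in fact divided between stems, say so; chi-squared may then stay. The Fisher test for reliability is not affected by this change.

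The cost is a few sentences, plus a short re-analysis if the tests have already been run, as the past tense of the section suggests. No new scans or planning are needed, and the percentages per stem do not change.

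### Fisher's test is the only method named for the reliability of the simulations, and it does not measure agreement

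*Combined protocol and SAP*

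**What the plan says.** The Statistical Analysis section has one sentence on reliability: "The reliability of the simulations was assessed using Fisher test (categorical variables". The comparison of categorical results is covered separately: "Qualitative data were expressed as frequencies and percentages and tested using chi-squared test". So, as worded, Fisher's test is not introduced as a small-cell substitute for chi-squared. Significance is set at 0.05.

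The study description gives 200 CT scans and, on that series, plans for "3 different types of hip stem designs using the 3D Hip-Op software". The main result is pass/fail: "The percentage of every stem design providing the optimal reconstruction in dysplastic hips (all the 5 parameters matched) will be assessed". Behind it lie parameters measured in degrees, per cent and centimetres and then cut at limits, among them "combined anteversion between 25°-50°, global offset not inferior to 12% of the native offset, leg lengthening not superior to 3 cm". These measurements are also to be examined in their own right: "The single parameters, especially the combined anteversion, the offset restoration and the leg lengthening, will be assessed for every simulation".

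Neither section mentions repeat planning, a second planner, a reference standard, or any agreement statistic.

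**The concern.** Every result in this study is a software plan classified against fixed limits, and the main outcome requires all five parameters to lie within them. A small planning error near one limit can change the class of the whole plan. A reader therefore needs to know how often a repeated plan would change class, and how large the measurement error is relative to limits such as 3 cm or ±5°.

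Fisher's test gives neither. There are two ways to apply it to repeated readings:

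- **On the cross-table of first against second reading**, a small p-value shows only that the readings are associated. That can happen with weak agreement, or with agreement worse than chance.
- **On the pass totals of the two readings**, the test ignores that both come from the same scans. A large p-value is only a failure to detect a difference, but it would be easy to report it as evidence of reliability.

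The sentence also restricts reliability to categories, so the error in degrees, per cent and centimetres is never quantified.

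**Working it through.** The documents give no agreement figure, pass rate or number of repeats, so there is no stated figure to reproduce. The check asks what Fisher's test would report at known levels of agreement.

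**Inputs.** From the documents: significance level 0.05 (two-sided is assumed, as sidedness is not stated) and 200 scans, which is the largest possible number of repeats per stem. Assumed: 70% pass on each reading, and 20 to 200 repeats.

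**Formulas.** For paired counts [[a, b], [c, d]] with n = a+b+c+d:

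- raw agreement po = (a+d)/n
- chance agreement pe = 0.7² + 0.3² = 0.58 at these margins
- kappa = (po − pe)/(1 − pe) = (po − 0.58)/0.42

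**Use (a): cross-table of two readings.** All tables with 70% margins were searched for the smallest positive kappa giving Fisher p<0.05.

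| n | Table | po | kappa | Fisher p |
|---|---|---|---|---|
| 20 | 12, 2 / 2, 4 | 0.80 | 0.52 | 0.037 |
| 30 | 18, 3 / 3, 6 | 0.80 | 0.52 | 0.008 |
| 40 | 23, 5 / 5, 7 | 0.75 | 0.40 | 0.021 |
| 50 | 28, 7 / 7, 8 | 0.72 | 0.33 | 0.040 |
| 100 | 54, 16 / 16, 14 | 0.68 | 0.24 | 0.031 |
| 200 | 105, 35 / 35, 25 | 0.65 | 0.17 | 0.028 |

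For example, at n=200: po = (105+25)/200 = 0.65 and kappa = (0.65 − 0.58)/0.42 = 0.17, with 95% CI 0.02 to 0.31. The agreement needed for significance falls as n rises. The pass rate matters little: at n=200 the smallest significant kappa is 0.16 with 50% passing and 0.17 with 90% passing.

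The p-value does not show direction either. With 100 of 200 passing on each reading, 90% agreement (90, 10 / 10, 90; kappa 0.80) and 90% disagreement (10, 90 / 90, 10; kappa −0.80) both give p = 6.7×10⁻³³. At 70% passing, the lowest attainable kappa is (0.40 − 0.58)/0.42 = −0.43. It gives p = 0.11 at n=20, 0.029 at n=30, 0.002 at n=50 and 4×10⁻¹² at n=200 (table 80, 60 / 60, 0).

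**Use (b): pass totals compared as independent proportions.** With 140/200 against 140/200, p = 1.0 whether the paired kappa is −0.43, 0 or 0.90, because the pairing never enters the test. Starting from 70% passing, the largest fall on the second reading that still gives p≥0.05 is:

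| n | Largest undetected fall | Percentage points |
|---|---|---|
| 20 | 7 of 20 | 35 |
| 50 | 10 of 50 | 20 |
| 100 | 14 of 100 | 14 |
| 200 | 19 of 200 | 9.5 |

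**The case against.** The strongest reply is that the check presupposes repeat readings the documents never describe. With one plan per stem per scan, reliability may be loose wording for something else, such as a comparison of pass rates between stems. That is possible, but it does not rescue the sentence: a between-stem comparison says nothing about agreement either, and chi-squared is already assigned to categorical comparisons.

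Three points of scope stand in part:

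- **The magnitudes are illustrative.** Pass rate and number of repeats are assumed. The kappa of −0.43 is the worst case at those margins and is unlikely when the same scan is re-planned; it shows a property of the test, not an expected result. Likewise, 0.17 applies only if all 200 scans are repeated.
- **Assessing a pass/fail outcome by category is not an error in itself.** Kappa with percent agreement would correct the named test. The analysis of continuous values is needed because the study description says the single parameters will be assessed for every simulation.
- **The consequence is limited.** No reliability objective or decision rule is stated, and reliability does not enter the stem comparison directly.

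**Conclusion.** The concern holds. The plan names a specific method for reliability, and that method does not measure it; this is a wrong choice of analysis, not just missing detail. Followed as written, it could declare reliability at a kappa of 0.17 (200 repeats) or 0.52 (20 repeats), or fail to notice a fall in pass rate of 9.5 to 35 points, depending on how the test is applied. These sizes rest on an assumed 70% pass rate and an assumed range of repeats. The conclusion does not: significance depends on n at any pass rate, and equal totals give p=1.0 at any n. The per-stem percentages are not invalidated by this point, but any statement that they are reproducible would be unsupported. It should be fixed.

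**What to change.** First state what reliability means here and which plans are compared. If repeat plans exist, replace the sentence with wording such as:

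> Reliability of repeated simulations ([number] scans, re-planned by [same/second] reader blind to the first plan) is assessed per stem design by Cohen's kappa with 95% CI and percent agreement for pass/fail outcomes, and by ICC (two-way, absolute agreement) with Bland-Altman limits for combined anteversion, offset, leg lengthening, tilt and canal fill.

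The brackets should be filled from the repeat design actually used. If no repeats exist, remove the reliability claim, or re-plan a subset.

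**Cost.** With repeats in hand: one or two sentences and a standard re-analysis of those plans. Without them: one deletion, or the reader time to re-plan a subset. The drawbacks are slightly more analysis work and a reported reliability that may look less favourable.

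### An unadjusted 0.05 chi-squared rule, with no confirmatory outcome named and pairing ignored, leaves the error rate off 5% in a direction the plan does not settle

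*Combined protocol and SAP*

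**What the plan says.** The unnumbered study description sets a within-scan design, with every stem simulated on each scan: "200 native pelvis and thigh CT scans performed in patients with hip dysplasia, 3 different types of hip stem designs". It describes the purpose as a percentage: "with the aim of analyzing, on the CT simulations, the percentage of adequate reconstruction of the optimal biomechanical parameters". Two kinds of outcome follow. One is the composite: "The percentage of every stem design providing the optimal reconstruction in dysplastic hips (all the 5 parameters matched) will be assessed". The other is the set of components: "The single parameters, especially the combined anteversion, the offset restoration and the leg lengthening, will be assessed for every simulation". Neither is called primary or secondary. The word of emphasis in the second sentence picks out three parameters but sets no order of testing.

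The Statistical Analysis section gives one rule for categorical outcomes, "Qualitative data were expressed as frequencies and percentages and tested using chi-squared test", and one criterion, "Threshold for significance: $p=0.05". Continuous measurements are summarised only: "Quantitative data were reported as average values, standard deviations and ranges of minimum and maximum". A separate Fisher test is named for reliability: "The reliability of the simulations was assessed using Fisher test (categorical variables". The section mentions no hierarchy, no adjustment, no paired test and no choice between a three-stem test and pairwise tests.

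**The concern.** Two features of the plan pull the error rate in opposite directions.

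- **Pairing is ignored.** The ordinary chi-squared test assumes independent groups. Here the same scan contributes a result for each stem. An anatomy that is hard for one stem is likely to be hard for the others, so results within a scan should be positively correlated, and the test then rejects too seldom.
- **The set of tests is open.** The rule covers all categorical data, so it can be applied to the composite alone or also to each parameter as pass/fail, and to three stems at once or in pairs. Each added test at 0.05 is another chance of a false positive.

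Suppose the composite shows no difference, but one parameter or one pair of stems gives p<0.05. The plan does not say which of these is the study's result. The choice could be made after seeing the data, and a reader could not tell how often such a finding would arise by chance. That problem exists whatever the correlation is.

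**Working it through.** **Inputs from the documents:** 200 scans; three stems on each; five parameters (sagittal and coronal tilt counted as one) plus one composite; threshold 0.05; ordinary chi-squared. No pass rates, correlations, power or effect size are given, so there is no figure of the plan's own to reproduce.

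**Possible test counts (inferred, not stated):**
- composite, three stems together: 1
- composite in pairs: 1 × 3 = 3
- composite and five parameters, three stems together: 1 + 5 = 6
- the same six outcomes in pairs: 6 × 3 = 18

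The Fisher reliability tests are left out of these counts.

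**Reference for independent tests,** 1 − 0.95^k: k=1, 5.0%; k=3, 14.3%; k=6, 26.5%; k=18, 60.3%. These tests are not independent, so the figures are illustrative only.

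**Effect of ignoring pairing.** Let φ be a common correlation between the pass/fail results of any two stems on one scan. With no true difference, the three-stem chi-squared statistic behaves approximately as (1 − φ) times a chi-squared variable with 2 degrees of freedom. The real size of a 0.05 test is then 0.05^(1/(1−φ)). For an assumed φ=0.2 this is 0.05^1.25 = 2.4%; for φ=0.5 it is 0.05^2 = 0.25%. A single planned test is therefore conservative.

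**Simulation with no stem differing.** Assumptions: pass rate per parameter 0.7 or 0.9; latent within-scan correlation between stems 0.3 to 0.8; correlation between parameters 0 or 0.3; 4,000 replicates per scenario. Chance of at least one p<0.05 with the planned chi-squared:

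| Within-scan correlation | Composite once | Three composite pairs | Six three-stem tests | 18 pairwise tests |
|---|---|---|---|---|
| 0.3 | 3.1-4.0% | 8.5-10.3% | 14.4-16.2% | 37.0-39.4% |
| 0.5 | 1.6-2.5% | 5.7-7.6% | 7.3-11.3% | 24.4-28.9% |
| 0.6 | 1.1-2.5% | 4.6-6.6% | 4.4-8.0% | 17.6-23.4% |
| 0.8 | 0.2-0.6% | 1.5-3.5% | 0.7-1.4% | 5.4-8.4% |

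Repeat runs agreed within about 2 points. At 0.3 they reached 4.7% for the composite tested once, 18.2% for six tests and 41.0% for 18.

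**If only the pairing were corrected.** On the same assumptions, six Cochran's Q tests without a hierarchy give about 24-27%, and 18 McNemar tests about 49-56%. The lower figures in the table come from the conservatism of an unsuitable test, not from control of multiplicity.

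**The proposed procedure.** Composite Q at 0.05 followed by gated McNemar tests gives 4.4-5.6%, and about 4-6% across runs. Three ungated McNemar tests on the composite give 11.3-12.7%. If one stem is truly worse by 10 or 20 points on one parameter, a false claim on the two equal stems after the gate occurs in 2.5-5.6%.

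**The case against.** The best defence is that the composite is evidently the main outcome. The study description uses it to define optimal reconstruction and lists it first, and the continuous measurements are only summarised. On that reading there is one tested composite plus description, and no inflation.

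This is plausible, and it rules out a stronger reading that a reader might infer: that the plan commits to 18 tests, or carries a false-positive rate of 41% or even 60%. The documents do not say so. With six tests and a within-scan correlation of 0.8, the planned method is well below 5%. The defence does not settle the matter, however. The stated purpose also speaks of percentages for the parameters, the chi-squared rule covers all categorical data, and a composite-only reading leaves three pairwise tests open (about 1-10%). Even when the composite is tested once, the test is wrong for paired data, only in the conservative direction.

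Other objections stand in part:
- **The sizes rest on assumptions.** On a wider grid (pass rates up to 0.97, stem correlation up to 0.95, parameter correlation up to 0.8), six Q tests gave about 18-28% and 18 McNemar tests about 40-56%. At stem correlation 0.5, the planned chi-squared gave about 6-14% for six tests and 20-35% for 18. The ranges shown belong to their stated grid.
- **A descriptive study needs no hierarchy.** True, and saying so would also resolve the point. The plan nevertheless sets a significance threshold.
- **Part of the document was not available.** It could label a primary outcome, so the claim is limited to the available text.

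A reader might also infer from the past tense that results had already been seen. It may be template wording, and the documents do not establish it either way.

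**Conclusion.** The concern holds in a conditional form. It is certain from the available text that an independent-groups test at an unadjusted 0.05 is applied to within-scan data, that no outcome is made confirmatory, and that the form of the stem comparison is not stated. The error rate is therefore neither 5% nor determinable from the plan.

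The direction is not fixed. For pass rates of 0.7-0.9, within-scan correlation of 0.3-0.8 and parameter correlation of 0-0.3, the chance of at least one false positive runs from about 0.2-4% (composite once, too conservative) through 1-10% (three composite pairs) and 1-18% (six tests) to 5-41% (18 tests). A flat statement that the plan inflates the error rate would go too far. What is supported is that the plan does not control it, and that the study's result could be chosen after the data are seen. The change is worth making; confidence is high on the omission and medium on its size.

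**What to change.** In the Statistical Analysis section:

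1. Name the composite as the single primary outcome.
2. Replace chi-squared with Cochran's Q across the three stems at 0.05, because all stems are planned on the same scans.
3. Make the three pairwise McNemar comparisons, each at 0.05, only if Q is significant.
4. Report the five single parameters descriptively: pass rate per stem and paired differences with 95% confidence intervals, with no significance claims.
5. State whether any results had been seen when this hierarchy was set. If they had, label the analysis as not prespecified.

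The cost is a few sentences and no new data. There are two losses. A single-parameter difference with an unadjusted p just under 0.05 can no longer be called significant, and no pairwise claim on the composite is possible if Q is not significant. If results have already been seen, the wording cannot restore prespecification; it can only make the status of the analysis clear.
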